## Study Design and Methods

**Methods:** *Describe, in detail, the research activities that will be conducted under this protocol:*

**Preoperative Visit and Anesthesiologist Assessment:** Patients meeting eligibility criteria will be approached during their surgical preoperative visit by the study coordinator in the clinic of the orthopedic Co-Principal Investigators. Those choosing to participate will be screened for inclusion and exclusion criteria. Patients will be assessed for ability to undergo a spinal anesthetic, but will be counseled that the decision between a spinal and general anesthetic will ultimately be determined by the anesthesiologist on the day of surgery. Thus, patients may be withdrawn on the day of surgery if the staff anesthesiologist does not agree with their candidacy to undergo a spinal anesthetic. Furthermore, patients will be counseled they may be withdrawn from the study if placement of a spinal anesthetic in the operating room proves unsuccessful and a general anesthetic is required.

**Randomization and Blinding:** Patients will be randomized in a 1:1 fashion. The first arm will be the "Mepivacaine" (70 mg) group and the second arm will be the "Low-Dose Bupivacaine" (10 mg) group. This trial will be conducted in a double-blinded manner. The patient and the postoperative outcomes assessors (PACU and Orthopedic Inpatient Nurses and Physical Therapists) will be the blinded parties. The anesthesia and surgical teams will not be blinded given they won't be responsible for any assessments. After a patient has been consented and enrolled, the study coordinator will randomize the patient to either Mepivacaine or Low-Dose Bupivacaine using a custom electronic randomization system which will be maintained by the study statistician. The surgical team and anesthesia team will be notified after the assignment is complete so the surgical listing can be completed with the appropriate medication.

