**In Hospital Evaluation:** A standardized study card will be used to track patients throughout their various phases of care. At the time of discharge, the cards will be returned to the study coordinator for data entry in a secure spreadsheet available only to study staff. The study will begin with the anesthesiologist recording the time the spinal anesthetic is administered. The anesthesiologist will also record the time of incision, time of surgical closure, and time leaving the OR. The PACU nursing staff will then record the time of PACU entry and exit as well as the status of lower extremity function in the non-operative lower extremity at 15 minute intervals. The choices will be Bromage 3 (no movement), Bromage 2 (ankle movement only), Bromage 1 (ankle and knee movement), Bromage 0 (ankle, knee, and hip movement). Once the patient transitions to the general inpatient floor, the nursing staff will be responsible for recording motor function in a similar fashion at 15 minute intervals until the patient achieves Bromage 0 status. The physical therapy team will be responsible for recording the time of the first physical therapy session and the distance the patient ambulates during this session. Additional data points to be recorded by nursing staff will be total opioid consumption in the first 24 hours after surgery, pain scores, presence of nausea and/or vomiting, presence of orthostatic hypotension, and length of hospital stay. TNS will be evaluated twice, once during hospitalization by either the orthopedic or anesthesia team rounding on the patient on post-operative day one and a follow-up phone call performed on POD 6-9 by a study member not blinded to patient assignment. A standardized questionnaire will be used to determine the presence of symptoms of backache. TNS will be defined as new onset of back pain that radiates

bilaterally to buttock or distally. Back pain that does not meet these criteria will not be considered TNS. (ref. Anesth Analg 2005;101:661-5)

**Follow-up Evaluation:** Assessment will only take place during the hospitalization for the intended surgery. There will be a single phone call during post-operative day 6-9 for assessment of TNS.

**Resources:** *Describe the available resources to conduct the research (personnel, time, facilities, mentor commitment, etc.):*

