#### Endpoints

**Primary:** Evaluate time to return of lower extremity motor function between mepivacaine and low-dose bupivacaine spinal anesthetic among patients undergoing primary THA and TKA. This will be assessed by measuring time from spinal anesthetic administration to postoperative achievement of Bromage 0 function (return of spontaneous ankle, knee, and hip movement) in the non-operative extremity.

**Secondary:** Evaluate postoperative outcomes potentially related to anesthetic administration including pain scores, opioid consumption, urinary retention, transient neurologic symptoms, length of PACU stay, length of hospital stay, time to participation in physical therapy and walking distance with physical therapy. This will be determined by nurse and physical therapy charting and review of the medical record.

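### The reason for unblinding the surgical team covers assessments but not care decisions, leaving hospital stay, and to a lesser degree opioid use and therapy start, exposed to bias of unknown size

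*Combined protocol and SAP*

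**What the plan says.** Under Randomization and Blinding the trial is described as double-blinded, and the blinded group is defined: "The patient and the postoperative outcomes assessors (PACU and Orthopedic Inpatient Nurses and Physical Therapists) will be the blinded parties". Two teams are left out, for one stated reason: "The anesthesia and surgical teams will not be blinded given they won't be responsible for any assessments". Both are then told the arm, for one stated purpose: "The surgical team and anesthesia team will be notified after the assignment is complete so the surgical listing can be completed with the appropriate medication".

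The secondary endpoints (Endpoints) include "length of PACU stay, length of hospital stay, time to participation in physical therapy and walking distance with physical therapy", with opioid consumption earlier in the same list. In Hospital Evaluation assigns the recording to blinded staff. For opioids: "Additional data points to be recorded by nursing staff will be total opioid consumption in the first 24 hours after surgery"; length of hospital stay is in the same nursing list. For therapy: "The physical therapy team will be responsible for recording the time of the first physical therapy session".

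The same section places an unblinded team on the ward after surgery. TNS is evaluated "once during hospitalization by either the orthopedic or anesthesia team rounding on the patient on post-operative day one".

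**The concern.** Blinding the person who writes down an outcome protects the outcome only if it is a rating or a reading. Hospital stay is different: it ends when someone decides to discharge the patient. Opioid use and the time of the first therapy session also depend in part on what is ordered and when. A blinded nurse who records a discharge time is recording somebody else's decision.

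The protocol's stated expectation has a direction. The hypothesis is that motor function returns faster with mepivacaine, and the Background links a shorter block to earlier therapy readiness, ambulation and discharge. The orthopedic surgeons are Co-Principal Investigators, so those told the arm include people who hold that hypothesis. A team that expects one arm to be ready sooner may act sooner in that arm.

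A difference in stay or therapy time could then come from the drug or from knowledge of the arm, and the planned t-test or Wilcoxon comparison could not separate the two. A larger sample would not help. Early therapy, length of stay and resource use are also what the Background gives as the motivation for the trial.

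**Working it through.** The plan gives no figure on this point, so there is none to reproduce. The check sets the relevant sections side by side.

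1. **Who knows the arm.** Known to: anesthesia and surgical teams. Hidden from: patient, PACU nurses, inpatient nurses, physical therapists (Randomization and Blinding).
2. **Who records.** Nurses record opioid use and hospital stay; therapists record the first session (In Hospital Evaluation). All are blinded, so measurement is protected.
3. **Who decides.** The documents do not say who decides discharge, analgesia or start of therapy. They give no discharge criteria, analgesic protocol or rule for starting therapy that would limit discretion, and assign none of these decisions to a blinded party.
4. **Whether unblinded staff are active after surgery.** Yes. The orthopedic or the anesthesia team rounds on day one.
5. **Whether the stated reason holds.** Not fully. It is silent on care decisions. It also conflicts with the day-one TNS evaluation, which one of those same teams carries out. Who scores TNS is a separate matter; it counts here because it weakens the only justification given.
6. **Whether the surgical team needs the arm.** The only use stated is completing the listing.
7. **Primary endpoint.** Time from spinal administration to Bromage 0, scored every 15 minutes by blinded nurses. Decisions on discharge, analgesia or therapy do not enter it.

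Exposure by endpoint, if the orthopedic team takes these decisions (assumption):

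| Endpoint | Decision behind it | Protection in the plan |
|---|---|---|
| Hospital stay | Discharge | Recorder blinded; decision not |
| Opioid use, 24 h | Analgesic orders | Patient and nurses blinded; partial |
| Time to first therapy | When therapy starts | Patient and therapists blinded; partial |

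**Sensitivity, on assumed shifts only.** Suppose there is no drug effect and knowledge of the arm shifts the mean of a continuous secondary endpoint by b standard deviations. With n = 150 per group (Sample Size) and a two-sided 5% test, the false-positive rate is approximately

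1 − Φ(1.96 − m) + Φ(−1.96 − m), where m = b / √(2/150) = 8.66 b.

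- b = 0.05: m = 0.433, rate about 7%
- b = 0.10: m = 0.866, rate about 14%
- b = 0.20: m = 1.732, rate about 41%

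The documents give neither b nor the standard deviation of any of these endpoints, so these rates show only how the error grows with the shift. They do not estimate what will happen in this trial.

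**The case against.** The strongest reply is that the mechanism is assumed. The documents never say that the surgical team writes discharge, analgesic or therapy orders; they show only that the orthopedic or the anesthesia team rounds on day one. That stands. A reader might infer that the surgical team's decisions do set hospital stay and that these endpoints are therefore biased. The documents support only an exposure that depends on who decides.

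Second, the primary endpoint and Aim 1 are untouched. That stands too, and this point should not be read as a criticism of the main comparison.

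Third, patients, nurses and therapists are all blinded, which limits how far knowledge of the arm can alter opioid use or the start of therapy. This stands in part. It ranks those two endpoints below hospital stay without removing the exposure.

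Fourth, a reader might want to size the bias against the 30-minute difference in the Sample Size section. That figure belongs to motor recovery, with its own standard deviation of 65.6 minutes, and says nothing about what matters for hospital stay. The larger rates in the sensitivity calculation have no support in the documents either.

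Finally, restricting the notice is not free of complications. Someone must still complete the listing, and the anesthesia team, which has to know the arm, may also be the team that rounds. These objections are fair, and the fix has to answer them.

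**Conclusion.** The concern holds in limited form. The stated reason for leaving the surgical team unblinded does not extend to care decisions, and the plan neither says who takes those decisions nor gives them to anyone blinded. If the orthopedic team takes them (assumption), length of hospital stay is exposed to bias from knowledge of the arm, and opioid use and time to first therapy are exposed to a lesser degree. The likely direction, if the team acts on the stated hypothesis, favors mepivacaine. The size is unknown and cannot be worked out from the documents.

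The change is worth making because it is specific and cheap, and because these outcomes carry much of the trial's practical rationale.

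**What to change.** In Randomization and Blinding:

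- Send the assignment only to the anesthesia staff who prepare and give the spinal. The coordinator or those staff supply the medication, and the surgical listing shows only a neutral entry such as 'study spinal'.
- State who decides discharge, analgesia and start of therapy. Add the orthopedic ward staff who do so to the blinded parties until the POD 6-9 call is complete, with provision for emergency unblinding.
- Where feasible, have anesthesia staff who know the arm take no part in those decisions.
- Where a decision-maker remains unblinded, report the affected endpoints as not protected by blinding.

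The cost is a protocol edit and a small workflow change: a different recipient list for the assignment notice and a masked listing. Residents and midlevel providers who help with enrollment (Resources) must be kept off the assignment notice if they also make ward decisions. Blinding of staff present in the operating room may be incomplete, but decision-makers who were not there can stay blinded. No visits or measurements are added.

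### Transient neurologic symptoms (TNS) have no blinded assessor: the day-one check goes to teams left unblinded because they supposedly assess nothing, and the later call is openly unblinded

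*Combined protocol and SAP*

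**What the plan says.** All the relevant text is in the combined protocol and SAP, mostly under Study Design and Methods.

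- **Who is blinded (Randomization and Blinding).** The trial is described as double-blinded, and "The patient and the postoperative outcomes assessors (PACU and Orthopedic Inpatient Nurses and Physical Therapists) will be the blinded parties".
- **Who is not blinded, and why (same paragraph).** "The anesthesia and surgical teams will not be blinded given they won't be responsible for any assessments". It adds that "The surgical team and anesthesia team will be notified after the assignment is complete".
- **Who randomizes (same paragraph).** "the study coordinator will randomize the patient to either Mepivacaine or Low-Dose Bupivacaine using a custom electronic randomization system".
- **First TNS assessment (In Hospital Evaluation).** It is made "once during hospitalization by either the orthopedic or anesthesia team rounding on the patient on post-operative day one".
- **Second TNS assessment (same paragraph).** It is "a follow-up phone call performed on POD 6-9 by a study member not blinded to patient assignment".
- **Instrument and definition (same paragraph).** "A standardized questionnaire will be used to determine the presence of symptoms of backache". TNS is then defined as back pain of new onset with bilateral radiation to the buttock or further down; other back pain does not count.
- **Role of TNS.** It is listed among the secondary outcomes in Research Question and Aims, in Endpoints and in Analysis, where binary outcomes are compared between arms at two-sided 0.05.

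**The concern.** The protocol gives one reason for leaving two clinical teams unblinded: they make no assessments. It then gives one of them, by name, and apparently the other, an assessment of a study outcome. Once the unblinded day 6-9 call is added, TNS appears to have no blinded assessor at any point.

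TNS is a reported symptom that someone has to ask about and classify, so it is open to detection bias. It is also the drug-related harm that the Background discusses at most length, and the Background states that bupivacaine has the lowest incidence. An assessor who knows the arm and shares that expectation may probe harder for symptoms after mepivacaine. One who wishes to see no difference may discount them. What is at stake is the credibility of the between-arm TNS comparison, in either direction.

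**Working it through.** **Text check.** The plan states no figure on this point, so the check sets the paragraphs side by side.

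| Item | Randomization and Blinding | In Hospital Evaluation |
|---|---|---|
| Anesthesia team | Unblinded, told the arm, said to make no assessments | May make the day-one TNS assessment |
| Surgical / orthopedic team | Unblinded, told the arm, said to make no assessments | May make the day-one TNS assessment |
| Day 6-9 caller | Not mentioned | Stated to be unblinded |
| Inpatient nurses | Blinded | Record other study data; TNS is not in their list |

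1. The anesthesia team is named in both paragraphs, so that half of the contradiction needs no interpretation. Reading the orthopedic team as the surgical team is an inference. The Resources section supports it: the surgeons there are orthopedic surgeons, and nurses and physical therapists are named separately.
2. The day 6-9 call does not contradict the stated reason for unblinding. It is a disclosed choice.
3. Count: two TNS assessments are specified, and 0 of 2 are made by a party listed as blinded.
4. Research Question and Aims and Endpoints say in general terms that secondary outcomes come from nurse and physical therapy charting and record review. That line covers eight outcomes and names no TNS assessor. The specific procedure is in In Hospital Evaluation, where the sentence beginning "Additional data points to be recorded by nursing staff" does not include TNS.

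**Illustration of what differential assessment could do.** The documents give no TNS rate for either study drug and no size of bias, so every rate below is assumed.

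Method: exact enumeration of two independent binomials with n = 150 per arm (Sample Size). With a and b cases in the two arms, s = a + b and N = 300, the smallest expected count is s/2. The test follows the Analysis section: Fisher's exact test if s/2 < 5 (assumed cut-off), otherwise Pearson chi-square without continuity correction (assumed),

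X² = N[a(150 − b) − b(150 − a)]² / [150 × 150 × s × (N − s)].

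The result is significant if two-sided p < 0.05. The probability of significance is the sum of Bin(a; 150, p1) × Bin(b; 150, p2) over all significant pairs (a, b).

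*Over-calling in one arm, equal true rates (p2 = p1 + excess):*

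| True rate | +0 points | +1 | +2 | +3 | +5 |
|---|---|---|---|---|---|
| 2% | 0.013 | 0.041 | 0.120 | 0.248 | 0.555 |
| 4% | 0.042 | 0.064 | 0.118 | 0.198 | 0.414 |

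*Under-calling in the higher arm (p2 = true rate × (1 − share missed)):*

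| True rates | 0% missed | 25% missed | 50% missed |
|---|---|---|---|
| 2% vs 8% | 0.687 | 0.402 | 0.120 |
| 4% vs 10% | 0.531 | 0.247 | 0.064 |

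For example, with half the cases missed, 8% becomes 8% × 0.5 = 4%, and power against 2% falls from 0.687 to 0.120. One point of over-calling leaves the rejection rate near the nominal 5% (0.041 and 0.064); larger distortions do not.

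**The case against.** **The patient is blinded and is the only source of the symptom.** The questionnaire is standardized and the definition is fixed, so the unblinded person merely asks and applies a rule. This stands as mitigation and is why the point is low in severity. It does not remove the problem: someone who knows the arm still asks about the pain and judges whether it is new and radiates as the definition requires.

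**The day 6-9 unblinding is disclosed, and the protocol says in parentheses whom it means by outcomes assessors.** This is correct. That call is a stated limitation, and the contradiction is confined to day one. But the unqualified double-blind label still does not describe how TNS is assessed.

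**The day-one remedy is partial.** If the later call stays unblinded, the overall TNS result still depends partly on unblinded elicitation. The documents also do not show that nurses or self-completing patients would apply the definition as well as rounding clinicians. Both remarks are fair. They limit the gain but do not justify leaving the text as it is: the reason given for unblinding is untrue as written, even if no assessor is changed.

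**The figures rest on assumed rates, and the striking ones need large distortions.** Agreed: 5 points on a true 2% is 7%, or 3.5 times the true rate. The conclusion places no weight on them.

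**Conclusion.** The concern holds. The two paragraphs contradict each other on the day-one TNS assessment, verbatim for the anesthesia team and by natural reading for the orthopedic team. Taken with the disclosed unblinded call, no blinded assessor elicits or classifies TNS at either time point.

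The size of any bias cannot be estimated from the documents, and its direction could go either way. The consequence is lower confidence in one of eight unranked, unpowered secondary comparisons. Time to Bromage 0 is recorded by blinded PACU and floor nurses, so the primary endpoint, the sample size and the primary analysis are unaffected. This is a low-severity point that should be fixed. It rests on the contradiction and the simple day-one remedy, not on the illustrative figures.

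**What to change.** 1. **Day one.** Have the orthopedic inpatient nurses, who are already blinded and already record study data, give the standardized TNS questionnaire on the study card, or have the blinded patient self-complete it. Reconcile Randomization and Blinding with In Hospital Evaluation, and align the general charting line in Research Question and Aims and in Endpoints. Cost: protocol wording and one more study-card item; no new visits or patients.
2. **Day 6-9 call.** If someone without access to the allocation is already available (not the coordinator, who randomizes), have that person make the scripted call and change the wording that describes the caller as unblinded. The documents do not show whether this is possible without added staff: the Resources section names surgeons, anesthesiologists, residents, midlevel providers, the coordinator and the statistician, and describes none of them as blinded.
3. **If no such caller exists.** Keep the call as planned, limit the double-blind statement to the outcomes it covers, state that the day 6-9 TNS assessment is not blinded, and interpret the TNS comparison with that limit. Cost: wording only.

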### Subject Information

*Target accrual is the proposed total number of subjects to be included in this study at Mayo Clinic. A "Subject" may include medical records, images, or specimens generated at Mayo Clinic and/or received from external sources.*

Target accrual: 300 patients

Subject population (children, adults, groups): Adult males and females

Inclusion Criteria:

1. Unilateral primary TKA or THA
2. 18+ years of age
3. Able to provide informed consent

Exclusion Criteria:

1. Body mass index (BMI) > 45 kg/m^2
2. Severe drug allergy\* to medications used in this study, including non-steroidal anti-inflammatory drugs (i.e. celecoxib and ketorolac), and local anesthetics.
  - *\*defined as an immune reaction resulting in shortness of breath, hives, anaphylaxis, wheezing, and fever*
  -
3. Contraindication to spinal anesthesia technique (e.g., known spinal stenosis, coagulopathy, sepsis, infection at site of injection, uncooperative, refusal, anticoagulation medications not held within appropriate time frame\*).
  - *\*Per ASRA guidelines, Clopidogrel (Plavix) held for at least 7 days, Dabigatran (Pradexa) held for at least 5 days, Rivaroxaban (Xarelto) held for at least 3 days, Warfarin (Coumadin) held for at least 5 days or recent INR of less than 1.4, Enoxaparin (Lovenox) with doses > 1 mg/kg held for close to 24 hours.*
4. Known to be currently pregnant or actively breastfeeding++
  - *++ Patients that have a previous history of menopause, hysterectomy, or tubal ligation will not be required to perform a pregnancy test. Female patients that do not meet this criterion will be asked to submit a urine sample, and will require a negative urine sample in order to proceed with study protocol. Urine sample be collected pre-procedurally.*
5. Impaired cognition
6. Lower extremity motor deficit

